10.3. Institutional review board (IRB)/Independent ethics committee (IEC)

Regarding MDV database, IRB/IEC approval is not required since MDV database comprised of unlinkable anonymized data.

10.4. Ethical conduct of the study

The study will be conducted in accordance with legal and regulatory requirements, as well as with scientific purpose, value and rigor and follow generally accepted research practice described in Ethical Guidelines for Medical and Health Research Involving Human Subjects.

11. MANAGEMENT AND REPORTING OF ADVERSE EVENTS/ADVERSE REACTIONS

In these data sources, individual patient data are not retrieved or validated, and it is not possible to link (i.e., identify a potential association between) a particular product and medical event for any individual. Thus, the minimum criteria for reporting an adverse event (AE) (i.e., identifiable patient, identifiable reporter, a suspect product, and event) cannot be met.

This study involves data that exist as structured data by the time of study start. In these data sources, individual patient data are not retrieved or validated, and it is not possible to link (i.e., identify a potential association between) a particular product and medical event for any individual. Thus, the minimum criteria for reporting an adverse event (AE) (i.e., identifiable patient, identifiable reporter, a suspect product, and event) cannot be met.

12. PLANS FOR DISSEMINATING AND COMMUNICATING STUDY RESULTS

In the event of any prohibition or restriction imposed (e.g., clinical hold) by an applicable competent authority in any area of the world, or if the party responsible for collecting data from the participant is aware of any new information which might influence the evaluation of the benefits and risks of a Pfizer product, Pfizer should be informed immediately.

All final data will be shared with BMSKK/BMS. It is also anticipated that results from this study will generate at least one study abstract for submission to a medical conference and one

manuscript for submission to an international peer-reviewed journal. The appropriate conferences and journal will be decided upon by the alliance medical team. Abstract, presentation materials (poster or slide deck) or a manuscript will be reviewed and approved both by Pfizer and BMS

14. LIST OF TABLES

None

15. LIST OF FIGURES

None

ANNEX 1. LIST OF STAND ALONE DOCUMENTS

None

ANNEX 2. ENCEPP CHECKLIST FOR STUDY PROTOCOLS

Not applicable

ANNEX 3. ADDITIONAL INFORMATION

Not applicable

1. AMENDMENTS FROM PREVIOUS VERSION(S)

Not applicable since this is the first version and no amendment

2. INTRODUCTION

Atrial fibrillation (AF) is characterized by a rapid, irregular heartbeat which can cause blood to pool in the atria and increase the risk of the formation of blood clots. AF affects 0.6% to 1.6% of the general population and up to 14% in cardiovascular clinics in Japan¹⁻³. AF can be categorized into three main categories based on patient characteristics: lone atrial fibrillation -AF in the absence of overt cardiovascular disease or precipitating illness non-valvular AF (NVAF) – presence of AF without concurrent rheumatic mitral valve disease or history of mitral valve repair or prosthetic heart valve; and secondary AF-AF that occurs in the setting of acute myocardial infarction (MI), cardiac surgery, pericarditis, myocarditis, hyperthyroidism, pulmonary embolism, pneumonia, or other acute pulmonary disease. Anticoagulation therapy is important to prevent thromboembolism in patients with NVAF. Warfarin, a vitamin K antagonist, is the first oral anticoagulant approved for the treatment and prevention of thromboembolism in Japan in 1962 and it had long been the only oral anticoagulant until the first non-vitamin K antagonist oral anticoagulants (NOACs), dabigatran, was introduced with approval for NVAF treatment in March 2011⁴. Apixaban was approved in December 2012 in Japan and demonstrated superiority compared to warfarin in preventing stroke or systemic embolism, caused less bleeding, and resulted in lower mortality in patients with atrial fibrillation in Phase 3 clinical trial⁵.

Although randomized control trials (RCTs) aimed at head-to-head comparison with placebo or a reference drug may provide evidence of safety and efficacy of treatments at the highest level, there are potential limitations derived from a limited number of pre-selected patients and strict patient eligibility criteria with regard to age, comorbidities, and concomitant medications. Accordingly, these studies may not accurately represent what happens when drugs are used in general clinical practice. Especially data for Japanese NVAF patients are limited due to limited number of Japanese patients recruited in the RCT. Also patients with higher risk from a safety perspective, for instance patients with active caner, are generally excluded from RCT and further limited data are existed. Previously we have shown that bleeding risks as well as stroke/SE risks are less in real world clinical practice in Japan compared to warfarin⁶⁻⁸, but there are still little data for Japanese NVAF patients who has higher bleeding risks such as components of HAS-BLED risk score factors, active cancer, uncontrolled hypertension etc. The objectives of this study is to compare the risk of incidence of

stroke and bleeding among NVAF patients with such higher bleeding risk(s) newly prescribed apixaban or warfarin using a nation-wide administrative claims database.

2.1. STUDY DESIGN

This is a retrospective observational study using data from Medical Data Vision Co. Ltd. (MDV Co. Ltd.) database (data set from 1 March, 2011 to 31 Jun, 2021). Among patients registered in the database, patients are selected based on the inclusion and exclusion criteria (see below).

Study measures include: (1) for safety evaluation: major bleeding (primary safety endpoint, defined as any bleeding requiring hospitalization for treatment); (2) for effectiveness evaluation: a composite of ischemic stroke, hemorrhagic stroke or SE (primary effectiveness endpoint).

The primary purpose of this study is to investigate the safety and effectiveness of apixaban compared to warfarin in patients who are prone to bleeding, with at least one known risk factor for bleeding. The analyses will be conducted using the 3-step procedure shown below,

First, all patients with NVAF who are newly diagnosed and initiated apixaban or warfarin will be extracted from the database. Among these patients, patients with at least one predetermined high bleeding risks will be extracted. In this study, predetermined high bleeding risks are 1) patients with hypertension diagnosis, 2) patients with liver dysfunction, 3) patients with renal dysfunction diagnosis, 4) patients with a history of bleeding, 5) patients with hemorrhagic stroke, 6) patients with alcohol abuse, 7) patients with concomitant used of antiplatelet drugs, 8) patients with chronic (continuously for longer than 90 days) concomitant use of Non-steroidal antiinflammatory drug (NSAID), 9) highly elderly (> 80 years old), 10) patients with refractory hypertension, 11) patients with a history of peptic ulcer diagnosis, 12) patients with active cancer, 13) patients with diabetes mellitus, 14) patients whose body weight is <40kg, 15) patients with polypharmacy (sea Section 5.4 for the definition). Patients with at least one predetermined high bleeding risk factor will be divided into two cohorts, apixaban and warfarin cohorts, based on the first prescribed drug just after the NVAF diagnosis. Patient characteristics will be balanced by using an inverse probability of treatment weighting (IPTW) method to create balanced apixaban and balanced warfarin cohorts. Comparisons will be conducted by using these balanced warfarin and apixaban cohorts (Kaplan-meier curves, incidence rates per 1,000 person-year and hazard ratio with 95% confident intervals). The primary safety and effectiveness analyses are comparison of apixaban with warfarin in patients with at least one predetermined risk factor for bleeding.

- Second, after the first analysis, we will conduct separate interaction analysis of the treatment (apixaban vs. warfarin) and one of the 15 risk factors (e.g., hypertension yes vs no, etc) to see if treatment effects are consistent among patients with or without each specific factor
- Third, patients will be stratified by risk factors into 15 subgroups, and same IPTW analyses as described in the step 1 will be conducted only in the subgroups with adequate sample sizes.

The follow-up period is variable, and will begin on the next day of the index date and continue until the earliest of the following scenarios – occurrence of target outcome event (details available in Subsection 5); discontinuation of apixaban or warfarin; switching from apixaban or warfarin; withdrawal from the database.

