2.2.4. Objectives of other exploratory analysis are

To explore the risk of major bleeding and stroke/SE in the specific populations at higher bleeding risk(s).

As shown above (see 2.1), after interaction analyses of the treatment and risk factors, patients will be stratified to subgroups by each of above mentioned 15 predetermined risk factors separately. Subgroups with adequate sample size will be selected for IPTW analyses.

In the previous feasibility analysis, we found that the numbers of patients with hemorrhagic stroke, alcohol abuse, chronic concomitant used of NSAIDs (for continuously > 90 days), and refractory hypertension were less than 2,000. Due to the insufficient statistical power, these subgroups could be eliminated from the further subgroup analysis. Again, the final decision will be based on the formal evaluation of the number of sample sizes N in those subgroups.

Candidates of exploratory subgroups listed based on the preliminary feasibility analysis

- Exploratory analysis regarding hypertension
- *Exploratory analysis regarding liver dysfunction.*
- Exploratory analysis regarding renal impairment.
- *Exploratory analysis regarding bleeding including intracranial hemorrhage*
- Exploratory analysis regarding concomitant use of antiplatelet drug
- *Exploratory analysis by age*
 - \checkmark > 80 y
 - \checkmark >90 y
- Exploratory analysis regarding peptic ulcer
- Exploratory analysis regarding active cancer
- *Exploratory analysis regarding low body weight (<40kg)*
- Exploratory analysis regarding diabetes mellitus
- *Exploratory analysis regarding polypharmacy (≥6 medicines)*

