10.3.6. Variables for subgroup analysis

Subgroups	ICD10 code	Standard disease code	Note
Hypertension			Refer to 10.3.1
Liver dysfunction			Refer to 10.3.1
Renal impairment			Refer to 10.3.1
	A162		Include only tubercular hemoptysis
	A165		Include only tubercular hemothorax
	B303		
	D500		
	D62		
	D66		Include only hemophiliac bleeding
	D683		Include only hemorrhagic disorder due to circulating anticoagulants
	D698		
	D699		
	E078		Include only tyroid bleeding
	E274		Include only adrenal bleeding
	G361		
Bleeding history	G951		Include only hematomyelia, spinal subdural hemorrhage, hematorrhachis, spinal epidural hemorrhage and spontaneous Cervical Epidural Hematoma
	G968		Include only spinal subarachnoid hemorrhage
	H052		Include only orbital fat hemorrhage
	H113		
	H168		Include only Hemorrhagic keratitis
	H208		Include only hemorrhagic iritis
	H210		
	H313		
	H350		Include only hemorrhagic retinitis and juvenile recurrent
			vitreoretinal hemorrhage
	H356		
	H357		Include only hemorrhagic retinal pigment epithelial detachment
	H405		Include only hemorrhagic glaucoma
	H431		

Subgroups	ICD10 code	Standard disease code	Note
	H448		Include only intraocular hemorrhage
	H470		Include only optic disc hemorrhage and optic nerve sheath hemorrhage
	H603		Include only otitis externa hemorrhagica
	H669		Include only hemorrhagic otitis media
	H738		Include only eardrum bleeding
	H922		
	I213		Include only Atrial thrombus as current complication following acute myocardial infarction
	I230		
	I312		
	I600		
	I601		
	I602		
	I603		
	I604		
	I605		
	I606		
	I607		
	I608		
	I609		
	I610		
	I611		
	I613		
	I614		
	I615		
	I616		
	I618 I619		
	1619 1620		
	1620 1621		
	I629		
	1629 1638		Inculde only hemorrhagic cerebral infarction
	1690		
	I691		
	1780		
	1788		
	1850		
	I864		Include only gastric variceal bleeding
	J041		Include only hemorrhagic tracheitis
	J339		Include only bleeding polyp
	J90		Include only hemorrhagic pleural effusion
	J942		
	J950		Include only bleeding from a tracheostomy site
	K049		Include only hemorrhage in the pulp
	K068		Include only gingival hemorrhage
	K121		Include only hemorrhagic stomatitis
	K137		Include only oral hemorrhage

Subgroups	ICD10 code	Standard disease code	Note
	K148		Include only tongue root submucosal bleeding
	K226		
	K228		Include only esophageal hemorrhage
	K250		
	K252		
	K254		
	K256		
	K260		Exclude acute gastroduodenal mucosal lesion
	K262		

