	S369		Include only hematoma
	S370		Include only hematoma
	S378		Include only hemorrhage
	S390		Include only hematoma
	S400		Include only hematoma
	S408		Include only hematoma
	S500		Include only hematoma
	S501		Include only hematoma
	S600		Include only hematoma
	S601		Include only hematoma
	S701		Include only hematoma
	S800		Include only hematoma
	S801		Include only hematoma
	S902		Include only hematoma
	T009		Include only hematoma and hemorrage
	T060		Include only spinal subarachnoid hemorrhage
	T090		Including only hematoma
	T093		Including only hematoma
	T140		Including only hematoma
	T144		Include only traumatic hematomyelia
	T145		Include only traumatic arterial hematoma
	T146		Include only Intramuscular hematoma
	T794		Include only traumatic hemorrhagic shock
	T810		Include only hematoma and hemorrage
	T811		Include only hemorragic shock
	T876		Include only hematoma
	T905		Include only sequelae after
Hemorrhage stroke			Refer to 10.3.1
-	E244		
	E52		Include only Alcoholic pellagra
	F100		
	G312		
A 1 1 - 1 - 1	G405		Include only alcoholic epilepsy
Alcohol abuse	G621		
	G701		Include only alcoholic neuropathy
	G721		
	H470		Include only alcoholic optic neuropathy
	I426		· • • •

Subgroups	ICD10 code	Standard disease code	Note
	K292		
	K70		
	K852		
	K860		
	T519		
Antiplatelet drug			Refer to 5.4
NSAIDs			Refer to 5.4
	F54		Include only psychogenic gastric ulcer
	K221		
	K227		Include only Barrett's esophagus
	K25		
Dantianlan	K26		
Peptic ulcer	K27		
	K28		
	K51		
	K626		
	K633		
Active cancer			Refer to 10.3.1
Diabetes mellitus			Refer to 10.3.1
Polypharmacy	Polypharmacy		Refer to 5.4

Page 56 of 56

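### The code list behind the active-cancer factor admits benign tumours, and the peptic-ulcer and bleeding-history lists admit conditions outside their names; the exploratory subgroups and interaction tests are mislabelled

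*SAP*

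**What the plan says.** SAP 2.1 builds the primary population in one step: "patients with at least one predetermined high bleeding risks will be extracted". Any one of 15 factors is enough. Three matter here: "4) patients with a history of bleeding", "11) patients with a history of peptic ulcer diagnosis" and "12) patients with active cancer". Step 2 of the same section tests the interaction of treatment with each factor, present against absent. Step 3 repeats the weighted analysis within each subgroup that is large enough. SAP 2.2.4 lists "Exploratory analysis regarding active cancer" among the candidates.

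The factors become data through the appendix:

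- **Cancer.** In 10.3.6 the row "Active cancer" refers to the Cancer list in 10.3.1. That list runs through the C codes and on through D00 to D48. No code in it carries an inclusion or exclusion note, although several other conditions in 10.3.1 do.
- **Bleeding history.** Code I213 carries the note "Include only Atrial thrombus as current complication following acute myocardial infarction".
- **Peptic ulcer.** Code K227 carries the note "Include only Barrett's esophagus". K221, K51, K626 and K633 are listed without any note.

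SAP 5.4 asks only for one diagnosis code in the baseline period. Its cancer row cites diabetes codes, a separate slip; correcting that wording would leave the 10.3.1 list in force.

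**The concern.** A code list decides who is studied, whatever the label says. In ICD-10, the system that the SAP uses, D10-D36 is the block for benign neoplasms. A patient whose only entry is a benign tumour would be counted as having active cancer. A patient with Barrett's esophagus would be counted as having had a peptic ulcer. A patient with an atrial thrombus would be counted as having bled.

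This matters most for cancer. Protocol 7 and SAP 2 both motivate the study partly by the exclusion of active-cancer patients from randomised trials. A subgroup that mixes them with benign-tumour patients does not fill that gap. The yes/no interaction test is blurred because its yes side contains patients without the factor. A broad list can also carry a subgroup past the size criterion in SAP 2.1 and 2.2.4 on patients who do not belong in it.

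Cancer and peptic ulcer are not among the propensity-score covariates in SAP 7.1.1. Within the cancer subgroup every patient is coded yes, so the balance check in 7.1.2 cannot show, on that variable, whether the benign/malignant mix differs between arms.

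**Working it through.** **1. Count of the Cancer list (SAP 10.3.1).** The SAP prints these codes without names, so the grouping rests on the ICD-10 block structure.

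| Block | Codes listed | Number |
|---|---|---|
| C (malignant) | C00-C26, C30-C34, C37, C38, C40, C41, C43-C58, C60-C76, C78-C85, C88, C90-C97 | 86 |
| In situ | D00-D07, D09 | 9 |
| Benign | D10-D25, D27-D36 | 26 |
| Uncertain behaviour | D37-D46, D48 | 11 |
| Total | | 132 |

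Benign share: 26/132 = 20%. All D codes: (9 + 26 + 11)/132 = 46/132 = 35%. These are shares of codes, not of patients. The list passes from C76 to C78, so C77 is absent. That error runs the other way: a patient coded only with C77 would be classed as having no cancer.

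**2. The other two lists.** The case rests on the SAP's own notes for I213 and K227, and on the ICD-10 meaning of K51 (ulcerative colitis), which the SAP does not print. I213 also stands in 10.3.5, the bleeding list for the major-bleeding endpoint. There it appears under its ICD-10 name, acute transmural myocardial infarction of unspecified site, without the note.

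**3. Reach into the primary population.** A challenged code changes entry only if the patient has none of the other 14 factors. Those include hypertension, diabetes, age over 80, antiplatelet use and six or more oral drugs. No document gives the number of such patients.

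**4. Power.** The plan's own figures first (SAP 7.1.9): HR 0.7, two-sided 0.05, power 0.80, 1:1.

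- Events (Schoenfeld): 4 × (1.960 + 0.842)² / (ln 0.7)² = 246.8; the plan gives 246.
- Major bleeding: mean rate (3.77 + 2.50)/2 = 3.135% per year; 246/0.03135 = 7,847; the plan gives 7,846.
- Stroke/SE: mean rate (2.77 + 1.79)/2 = 2.28% per year; 246/0.0228 = 10,789, as in the plan.

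Dividing by an annual rate implies one year of follow-up per patient. Now assume that a fraction f of the primary population is wrongly admitted and has the CER3 all-patient rates (bleeding 2.81 and 1.69, stroke/SE 2.87 and 1.55% per year):

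| f | N, major bleeding | N, stroke/SE |
|---|---|---|
| 1% | 7,869 | 10,793 |
| 5% | 7,959 | 10,806 |
| 10% | 8,075 | 10,823 |
| 20% | 8,316 | 10,856 |

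For f = 20%, bleeding: warfarin 0.8 × 3.77 + 0.2 × 2.81 = 3.578; apixaban 0.8 × 2.50 + 0.2 × 1.69 = 2.338; 246/0.02958 = 8,316. The SAP expects more than 10,000 patients per cohort, hence over 20,000. Removing 20% would still leave 0.8 × 20,000 = 16,000, above 10,789.

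**5. What mixing does to a subgroup hazard ratio.** Illustration only; the rates and hazard ratios by factor status are assumed. Take a warfarin bleeding rate of 3.77 with the factor and 2.81 without it, HR 1.0 with it and 0.7 without it, and the same contamination f in both arms. The apparent HR is about

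[(1 − f) × 3.77 × 1.0 + f × 2.81 × 0.7] / [(1 − f) × 3.77 + f × 2.81].

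This gives 0.98, 0.93 and 0.87 for f = 10%, 30% and 50%. If the hazard ratio is the same with and without the factor, mixing leaves it unchanged and only the event rates shift.

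**The case against.** The strongest reply is that little hangs on this. SAP 3.2 and 7.1.7 make the subgroup analyses exploratory, with no conclusions to be drawn. Protocol 9.9 already names misclassification of risk factors as a limitation. The same coding rule applies in both arms, and cancer does not enter the propensity model. This argument stands as far as severity goes. It does not excuse a label that the list contradicts: 9.9 speaks of claims diagnoses that may be wrong, not of a list that includes the wrong conditions by design.

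Three narrower points also stand:

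- The I213 note may be a translation fault. SAP 10.3.5 describes a search on Japanese words for bleeding and haematoma followed by hand editing, so deleting the code unseen could remove a valid entry.
- The peptic-ulcer list may be meant as a broad gastrointestinal-ulcer list. Then the label is at fault, and one criterion should govern every code.
- Keeping in-situ and uncertain-behaviour codes is a matter of judgement. Removing benign codes also does not make the remaining cancers active, since one diagnosis in the baseline period still qualifies.

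A reader might infer that the primary population as a whole is mis-selected, or that the apixaban-warfarin comparison is biased. The documents do not support either. Entry changes only for patients with no other factor, no count of them is given, and nothing shows that they differ by arm. A reader might also take 20% of codes as 20% of patients, or attach a percentage to the understatement of event rates. That would need the share of benign-only patients and their bleeding rate, and the documents give neither.

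**Conclusion.** The lists are wrong as written for the exploratory cancer, peptic-ulcer and bleeding-history analyses. The benign block is the main fault: 26 of 132 categories, unrestricted, under a factor called active cancer. I213 and K227 are single codes and minor beside it. Patients without the named factor enter these subgroups and the interaction tests, so the active-cancer result cannot be read as evidence in cancer patients.

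The number of patients affected cannot be computed from the documents. The effect on the primary population is limited to patients without any of the other 14 factors. It is probably small because several of those factors are broad, but that is a judgement and not a documented figure. On the plan's own arithmetic, power is not threatened even at an assumed 20% wrongly admitted. The conclusion rests on the ICD-10 meaning of the D codes, C77 and K51, and on the SAP's own notes for I213 and K227. Severity: should be fixed before extraction.

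**What to change.** Before data extraction, amend the SAP as follows:

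- **Cancer (10.3.1):** delete D10-D36 and add C77. Report D00-D09 and D37-D48 separately, or justify keeping them. State what makes a cancer active, or use the plainer label of cancer diagnosis that SAP 4.4 already carries.
- **Peptic ulcer (10.3.6):** remove K227 and K51, or relabel the factor. Either way, apply one stated criterion to the whole list, including K221, K626 and K633.
- **Bleeding (10.3.6 and 10.3.5):** check the Japanese disease name behind I213, then correct the note or remove the code in both places.
- **Use:** apply the corrected lists to entry, interaction tests and subgroups alike. Report how many patients would have qualified only through the removed codes; this supplies the figure that the documents lack.

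The cost is a code-list edit and one extra count. The cancer and peptic-ulcer subgroups become somewhat smaller, and their adequacy should be judged on the corrected numbers. The sample-size calculation need not change on this ground.

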3.2. STATISTICAL DECISION RULES

For primary safety and effectiveness analyses, all statistical tests will be performed at p=0.05 (twosided) with no adjustment for multiplicity. Since we will conduct various multiple subgroup analyses, which lead to the "Multiple Testing Problem". Here these subgroup analyses will be conducted with an exploratory purpose and we do not plan to conclude anything from the results here. Therefore, we will not adjust the p values and still the use p<0.05 to indicate the statistical significance.

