7.1.9. Power calculation

Incidence rates of stroke/SE and major bleeding in the primary analysis population here (that is, de novo NVAF patients initiating an anticoagulant therapy with warfarin or apixaban who have at least one bleeding risk factor) have not been investigated yet and hazard ratios of stroke/SE and major bleeding in apixaban users relative to warfarin users also have not been investigated yet. Therefore, we estimated the needed sample size to achieve adequate statistical power (e.g., 0.80) based on the major previous RCT and RWE conducted so far.

Study	Subgroup	HR	Incidence rate (%/year)	
			Warfarin	Apixaban
ARISTOTLE	-	0.79	1.60	1.27
	≥ 75 years		2.2	1.6
	≤ 60kg		3.2 2.0	
	Prior stroke or TIA		3.2 2.5	
	Diabetes		1.9	1.4
	Severe to moderate renal dysfunction		2.7	2.1
	Aspirin		1.9 1.3	
CER3		0.66	2.87	1.55

Stroke/SE

≥ 80 years	4.04	2.06
< 60 kg	3.47	2.45
Severe to moderate renal dysfunction	2.50	1.33
Anti-platelet	3.61	1.93

Major bleeding

Study	Subgroup	HR		nce rate year)
			Warfarin	Apixaban
ARISTOTLE	-	0.69	3.09	2.13
	≥ 75 years		5.2	3.3
	≤ 60kg		3.0	2.1
	Prior stroke or TIA		3.9	2.8
	Diabetes 3.1		3.1	3.0
	Severe to moderate renal dysfunction		6.4	3.2
	Aspirin		3.7	2.7
CER3		0.74	2.81	1.69
	≥ 80 years		3.94	2.35
	< 60 kg		3.67	2.61
	Severe to moderate renal dysfunction		3.32	2.21
	Anti-platelets		3.07	1.91

As shown in Tables above, absolute incidence rates of stroke/SE and major bleeding could be higher in patients with (a) risk factor(s) associated with bleeding. However, the ARISTOTLE study has revealed that P-value for interaction was mostly >0.05 and relative risk (HR) may not be changed in the specific subgroups compared to the entire cohorts

Based on the incidence rates and HRs shown above, sample size required for adequate statistical power (e.g., power=0.8) was estimated as follows,

Sample size calculation

	Assumption: Values used for calculation	Calculated results
For major bleeding		
Type I error rate	0.05	
Type II error rate	0.2	
Hazard ratio*	0.7	
N ratio in apixaban and warfarin cohorts	1:1	
Event rate for warfarin	3.77%/year**	
Event rate for apixaban	3.77%/year** 2.50%/year**	
Total events needed		246***
Estimated number of patients		7,846
	PFIZER CONFIDENTIAL	

Page 20 of 56

For Stroke/SE		
Type I error rate	0.05	
Type II error rate	0.2	
Hazard ratio*	0.7	
N ratio in apixaban and	1:1	
warfarin cohorts		
Event rate for warfarin	2.77%/year**	
Event rate for apixaban	2.77%/year** 1.79%/year**	

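### SAP step 2 asks whether the apixaban effect is consistent across 15 risk factors, but plans no interval for the interaction; p>0.05 cannot show consistency and would often miss complete loss of benefit, usually so for uncommon factors

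*SAP*

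**What the plan says.** SAP 2.1 sets out three steps. Step 1 is the primary comparison. Step 2 is a separate treatment-by-factor interaction analysis for each of the 15 factors, "to see if treatment effects are consistent among patients with or without each specific factor". Step 3 gives weighted subgroup analyses where the sample is adequate. SAP 2.2.4 places the interaction analyses under the exploratory objectives.

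SAP 3.2 gives the threshold. Primary tests are at two-sided 0.05. For subgroup analyses it says "we will not adjust the p values and still the use p<0.05 to indicate the statistical significance", after stating that "these subgroup analyses will be conducted with an exploratory purpose and we do not plan to conclude anything from the results here". Step 2 is not named there. SAP 7.1.7 repeats the disclaimer and plans subgroup HRs with 95% CIs. No section defines consistency, plans an interval for the ratio of hazard ratios, or gives power for an interaction.

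On the four rarest factors (fewer than 2,000 patients each), SAP 2.2.4 says: "Due to the insufficient statistical power, these subgroups could be eliminated from the further subgroup analysis". It leaves the final decision open, while protocol section 8 says they will not be included. Step 2 covers all 15 factors.

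SAP 7.1.9 notes of the earlier RCT that "P-value for interaction was mostly >0.05 and relative risk (HR) may not be changed in the specific subgroups compared to the entire cohorts".

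The summary table in SAP 7.2.3 has one interaction row: any high bleeding risk against none, in unbalanced patients. It has no rows for the 15 factors.

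**The concern.** Whether an effect is the same with and without a factor is an equivalence-type question. A test of no interaction answers a different one, and p>0.05 can mean either a similar effect or too few events. An interaction needs more events than a main effect of the same size, and the SAP's power calculation covers only the main effect.

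The sentence in 7.1.9 shows how easily the step from p>0.05 to an unchanged HR is made. The study is meant to inform clinicians about patients prone to bleed, and a statement that effects were consistent across risk factors is one they would act on. For the rare factors that may be dropped from step 3, no subgroup HR would be there to show how imprecise the result is.

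**Working it through.** **Inputs from SAP 7.1.9.** HR 0.7; two-sided 0.05; power 80%; 1:1; rates 3.77 and 2.50%/year for bleeding (mean 3.135%) and 2.77 and 1.79%/year for stroke/SE (mean 2.28%); more than 10,000 eligible patients per cohort, so 20,000 as a floor. Maximum follow-up is 2 years (SAP 4.1.3.1).

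**Assumed, because not given.** Mean follow-up of 0.5 to 2 years; factor prevalence f of 10% to 50%; events split in proportion to f; no precision lost to weighting.

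**The plan's own figure.** Events (Schoenfeld) = 4(1.96 + 0.8416)² / (ln 0.7)² = 246.8, against 246 in the SAP. Then 246/0.03135 = 7,847 and 246/0.0228 = 10,789, against 7,846 and 10,789. The plan's figures are reproduced, and its N implies 1 year per patient.

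**Interaction.** Complete loss of benefit means HR 0.7 without the factor and 1.0 with it: ratio of HRs 1/0.7 = 1.43, log 0.3567. With D total events,

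SE = √(4 / (D f(1−f))); power = Φ(0.3567/SE − 1.96) + Φ(−0.3567/SE − 1.96); miss rate = 1 − power.

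Example, bleeding, 20,000 × 1 year, f = 0.10: D = 20,000 × 0.03135 = 627; SE = √(4/56.43) = 0.266; 0.3567/0.266 = 1.34; power 27%; miss rate 73%.

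Miss rates, bleeding / stroke/SE:

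| Scenario | Events | f = 10% | f = 20% | f = 50% |
|---|---|---|---|---|
| Planned events | 246 | 87% | 80% | 71% |
| 20,000 × 0.5 year | 314 / 228 | 84 / 87% | 76 / 81% | 65 / 73% |
| 20,000 × 1 year | 627 / 456 | 73 / 79% | 57 / 67% | 39 / 52% |
| 20,000 × 2 years | 1,254 / 912 | 53 / 63% | 29 / 42% | 12 / 23% |
| 38,238 × 1 year | 1,199 / 872 | 54 / 65% | 30 / 44% | 13 / 25% |

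The last row uses the size of the previous study in protocol 9.5 (15,902 + 22,336). A 90% factor behaves like a 10% factor.

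**Events for 80% interaction power.** 246.8 / (f(1−f)) = 987 at 50% and 2,742 at 10%, that is 4 and 11 times the main-effect requirement.

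**Sensitivity, 20,000 × 1 year.**
- Poisson variances by cell instead of proportional events: power at 10% / 50% is 31 / 64% for bleeding and 24 / 51% for stroke/SE, close to the table.
- Assumed weighting variance inflation of 1.3 to 1.5: power over f = 10% to 50% falls to 19–50% and 15–39%.
- Overall HR held at 0.7, so that patients without the factor do better than 0.7: power at 10 / 20 / 30 / 50% rises to 36 / 66 / 86 / 99% and 28 / 53 / 75 / 96%.

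**What an interval would show.** For 2,000 patients with the factor among 20,000 followed for 1 year, the 95% limits are the estimate times or divided by exp(1.96 × 0.266) = 1.69 for bleeding, and 1.84 for stroke/SE. An estimate of exactly 1.00 for bleeding would carry limits of 0.59 and 1.69, which include 1.43.

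**The case against.** The case against has several sound parts.

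- **No rule is written.** Nowhere does the SAP say that p>0.05 will be reported as consistency. The p<0.05 threshold and the disclaimer stand together in 3.2: if one governs step 2, so does the other. This stands, and it is why 3.2 should say which applies. It does not supply what step 2 lacks, since judging consistency remains its stated purpose.
- **The 7.1.9 sentence is hedged** and supports a sample-size assumption. Also true. The crude RCT bleeding rate ratios in the same section run from 3.2/6.4 = 0.50 (renal dysfunction) to 3.0/3.1 = 0.97 (diabetes). Without event counts they do not show real heterogeneity; they show only that such p-values leave wide differences open.
- **Intervals exist elsewhere.** Step 3 gives subgroup HRs with CIs, and SAP 4.4 lists most subgroups as yes or no. But this applies only where size is adequate, and two separate intervals are not an interval for their ratio.
- **Power may be good.** For common factors with long follow-up, a larger cohort, or the overall HR held at 0.7, it is. This limits the claim about misses, but not the point that a non-significant test cannot show sameness.

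A reader might infer that these tests would usually miss a lost benefit, or that the plan would yield a finding of consistency whatever the truth. The documents do not support that. They give neither prevalence nor mean follow-up, 20,000 is a floor, and for bleeding with a 50% factor the miss rate is 39% at 1 year and 12% at 2 years.

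**Conclusion.** The point holds in a limited form. Step 2 asks about consistency with no planned interval for the interaction and no interaction power, and a non-significant test cannot answer it. That conclusion needs no power figure.

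The size depends on assumptions. Complete loss of benefit would be missed more often than not at the planned 246 events for any prevalence, and for factors near 10% or rarer in every scenario tabulated. For common factors the miss rate ranges from 71% at the planned events down to 12% (bleeding) and 23% (stroke/SE) at 20,000 × 2 years. All figures rest on HR 0.7 against 1.0, the SAP's mean rates, 1:1 arms and unweighted precision.

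The analyses concerned are exploratory; the primary comparison is not touched.

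**What to change.** 1. In SAP 2.1 (step 2) and 7.2.3, report for each factor and each primary endpoint the ratio of hazard ratios (with the factor / without it) with its 95% CI, beside the HRs in both strata.
2. In 3.2, state that interaction p>0.05 is not evidence of consistency, and that the exploratory disclaimer covers step 2.
3. For factors with fewer than 2,000 patients, show the estimate and CI only.
4. In 7.1.9, word the unchanged HR in subgroups as an assumption, not as an inference from p-values.
5. Reconcile step 2 with the interaction row in 7.2.3: which interaction is tested, whether it is weighted, and rows for the 15 factors.

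A fixed consistency margin is not required. With a range of 0.70 to 1.43 at 20,000 × 1 year and a 50% factor, even a truly constant effect would be called consistent for bleeding only 21% of the time: SE 0.160, 0.3567 − 1.96 × 0.160 = 0.044, and 2Φ(0.044/0.160) − 1 is about 21%. It would never be for stroke/SE, where 1.96 × 0.187 exceeds 0.3567, or for any 10% factor.

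Cost: SAP wording, one output column, and table rows for the 15 factors; no new data. The downside is less favourable wording where intervals are wide.
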